## 5. DEMOGRAPHICS AND BASELINE CHARACTERISTICS

Demographics and baseline characteristics including sex, race, ethnicity, age (both continuous and categorized: 6-9 years and 10-12 years), baseline weight (kg), height (cm), and BMI (kg/m^2) will be summarized by treatment group and overall for the safety and ITT populations. Sex, race, age group, and ethnicity will be summarized using summary statistics (n and percentage) for categorical variables. Age, baseline height, baseline weight, and baseline BMI will be summarized using summary statistics (n, mean, standard deviation, median, minimum, and maximum) for continuous variables. Demographic and baseline characteristics will also be provided in a listing by subject.

### 5.1 Prior, Concomitant, and Post-Treatment Medications

Prior medications are defined as the following:

- Medications with a start date prior to the first date of study drug.

Concomitant medications are defined as the following:

- Medications with a start date prior to the first date of study drug and with a stop date after the first date of study drug, or
- Medications with a start date prior to the first date of study drug and is ongoing, or
- Medications with a start date on or after the first date of study drug, and on or prior to the last date of study drug.

Post treatment medications are defined as the following:

- Medications with a start date after the last dose of study drug, or
- Medications with a start date on or prior to last date of study drug and is ongoing, or
- Medications with a start date on or prior to last date of study drug and stop date after last date of study drug

All medications will be coded using World Health Organization drug dictionary (WHO DRUG E, 2016 Q1 version). Medications with partial start and/or end dates will be described as prior, concomitant, or post-treatment medications by using available non-missing information. Medications with completely missing start dates (i.e., missing information for medication start day, month, and year) are assumed to be both prior and concomitant medications.

The frequency and percentages of subjects using prior, concomitant, and post-treatment medications at any stage of the study will be summarized according to the

WHO-DD Anatomical Therapeutic Chemical (ATC) classification Level 2 and preferred term, by treatment group for the safety population. The ATC levels will be presented in decreasing order of the total number of subjects (frequency). The ATC levels with the same frequency will be presented alphabetically. Preferred terms within each ATC level will be presented in decreasing order of the total number of subjects (frequency). The prior and concomitant medications will also be presented in listings by subject.

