10.3.1. Prohibited Medications

Subject must not have taken any of the following medications within the timeframe listed:

- Anticonvulsants for seizure control within 2 years prior to screening
- Antipsychotic medication within 6 months prior to screening
- Herbal or complementary treatments, eg, St. John's Wort, within 6 months prior to Day 1
- Any antidepressant medication (eg, bupropion, SSRI/ SNRI, tricyclic, etc) within 6 months prior to Day 1
- MAO inhibitor at any time
- Non-stimulant product as treatment for ADHD within 4 weeks prior to the start of screening.

Any subjects receiving stimulant medication for ADHD will discontinue that ADHD treatment for 3 - 5 days prior to Day -1 in order to ensure that there is at least a 72-hour washout before the assessment of ADHD symptoms on Day -1. Treatment with any ADHD medication is prohibited during the washout period. In addition, all subjects are required to refrain from other prohibited medications for at least 7 days, unless otherwise specified, prior to the first dose of study drug.

Use of any of the following medications is not permitted during the study from screening through the EOS visit:

- Lithium (any lithium preparation or formulation)
- Alpha-2 adrenergic receptor agonists (including clonidine and guanfacine), modafinil, armodafinil, atomoxetine, or any non-stimulant class agent
- Antidepressant medications (eg, bupropion, SSRI/SNRI, MAO inhibitor, tricyclic, etc)
- Anticonvulsant medications (eg, phenytoin, carbamazepine, lamotrigine, valproic acid, etc) and antipsychotic medications
- Pseudoephedrine-containing medications
- Medications with significant effect on blood pressure or heart rate. Intermittent use of asthma treatments is permitted but should be discussed with the medical monitor.
- Sleep aids with the exception of melatonin
- Diphenhydramine except topical formulations
- Herbal or complementary treatments, eg, St. John's Wort
- CYP2B6 substrates or inhibitors or inducers of CYP2B6 (see [Section 23](#), Appendix IV).

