15.3.6.6. Concomitant Medications

All medications will be coded using World Health Organization drug dictionary (WHO-DD).

The prior medications will include medications reported by the subject that started within 30 days prior to screening. The concomitant medications will include medications started on or after the first dose date of study drug

Frequency counts and percentages of previous and concomitant medications will be presented by the WHO-DD Anatomic Therapeutic Chemical (ATC) classification and preferred term for each subject group.

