Subjects will be confirmed as meeting DSM-5 criteria for a diagnosis of ADHD. Subjects may be either currently untreated or receiving stimulant ADHD medication at Screening. On Day -7 the ADHD Rating Scale Version IV - Home Version (modified for investigator administration) (ADHD-RS-IV HV) will be completed and subjects will attend a half-day practice laboratory classroom session intended to familiarize them with classroom schedules and procedures related to SKAMP evaluations, PERMP tests, and other planned activities. Any subjects receiving stimulant medication for ADHD will discontinue that ADHD treatment for 3-5 days prior to Day -1 in order to ensure that there is at least a 72-hour washout before the assessment of ADHD symptoms on Day -1. The day before randomization, the subject's parent/legal guardian will be contacted by study site staff in order to confirm the presence of clinically significant ADHD symptoms since discontinuation of stimulant medication. Clinically significant is defined as an ADHD-RS-IV HV total score  $\geq 26$  following a minimum 72-hour washout from any prior ADHD treatment. Subjects who do not demonstrate clinically significant ADHD symptoms (i.e., ADHD-RS-IV  $\geq 26$ ) on Day -1 will be considered screen failures and will not be eligible for randomization.

**Double-blind Period:** On Day 1 subjects will return to the clinic in the morning and those meeting all inclusion and no exclusion criteria will be randomized (1:1) to receive 2 mg/day dasotraline, or placebo, and will attend classroom sessions in which they will be evaluated for ADHD symptoms using the SKAMP assessment. During this baseline classroom assessment (Day 1), subjects will be evaluated at regular intervals: approximately 8 AM, 10 AM, 12 PM, 2 PM, 4 PM, 6 PM, and 8

[figure not shown]

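### SAP 5.1 counts a medication with a wholly missing start date as concomitant even when its known stop date is before the first dose

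*SAP*

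**What the plan says.** SAP 5.1 gives three ways for a medication to be concomitant:

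- "Medications with a start date prior to the first date of study drug and with a stop date after the first date of study drug";
- "Medications with a start date prior to the first date of study drug and is ongoing";
- "Medications with a start date on or after the first date of study drug, and on or prior to the last date of study drug".

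Two sentences then deal with incomplete dates. For partial dates: "Medications with partial start and/or end dates will be described as prior, concomitant, or post-treatment medications by using available non-missing information". For start dates that are missing altogether: "medication start day, month, and year) are assumed to be both prior and concomitant medications". The second sentence has no exception.

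The classification feeds a frequency table by treatment group in the safety population, and by-subject listings of prior and concomitant medications.

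On stimulants, SAP 2.2 has treated children "discontinue that ADHD treatment for 3-5 days prior to Day -1 in order to ensure that there is at least a 72-hour washout", and Protocol 10.3.1 has the same requirement. Protocol 10.3 makes both the start date and the stop date CRF fields, and Protocol 11.1 collects the same data for drugs taken in the 30 days before consent. Protocol 15.3.6.6 has its own, narrower definition: "The concomitant medications will include medications started on or after the first dose date of study drug".

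**The concern.** Assuming that an undated medication may overlap treatment is a normal conservative convention when overlap is possible. Here the rule also applies when the stop date rules overlap out. The record is then given a label that no value of the missing start date could justify.

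The exposed records are foreseeable. Children may enter on a stimulant, they must stop it before Day -1, and a parent may not recall when a long-standing drug was begun. The Protocol synopsis lists stimulants among the drugs not permitted from screening through the end-of-study visit. A stimulant row in the concomitant table would therefore suggest prohibited use during double-blind treatment when the drug had been stopped as required. Any other short course completed before dosing would be counted in the same way.

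**Working it through.** No sample-size or power figure is involved. The check sets the missing-start rule against SAP 5.1's own definitions.

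**Inputs.** The first dose is on the evening of Day 1 and the last dose on Day 14 (SAP 2.2 and 2.5). A stimulant stopped 3 to 5 days before Day -1 stops at about Day -4 to Day -6, since -1 - 3 = -4 and -1 - 5 = -6.

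**Definitions in symbols.** With start S, stop E, first dose F = 1 and last dose L = 14, a medication is concomitant if (S < F and E > F), or (S < F and ongoing), or (F ≤ S ≤ L).

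**Test.** For each known stop date, every possible true start (S ≤ E) was tried, and the result was compared with the missing-start rule, which always returns concomitant.

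| Known stop | Concomitant under the definitions? | Missing-start rule |
|---|---|---|
| Before first dose (Days -30, -6, -5, -4, -1) | Never, for any possible start | Wrong every time |
| Day 1 | Only if the start is also Day 1 | Conservative assumption |
| Days 2, 10, 14 | Always | Right |
| Day 20, or ongoing | Only if the start is on or before Day 14 | Conservative assumption |

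The first row follows directly. If E < F then S ≤ E < F. The first definition fails because E is not after F, the second because the drug is not ongoing, and the third because S is before F. The fault is confined to that row.

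**Two illustrative records.** Both are methylphenidate stopped on Day -5. With a start date of 1 January 2016 the record is prior only. With no start day, month or year it is prior and concomitant. The only difference is a missing field that cannot change the answer.

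**Does other text rescue it?** The sentence on using available information is limited to partial dates, and wholly missing start dates have their own sentence. Protocol 15.3.6.6 would not count the record either, because a drug stopped before the first dose did not start on or after it. SAP 12.2 declares no change from the protocol's planned analysis.

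**Comparison within the SAP.** The adverse event definition in SAP 8.4 handles the parallel case with the missing condition: an event with no start date counts if its stop date is on or after the first dose, or if both dates are missing.

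**The case against.** The strongest reply is that this is an edge case in a descriptive table. Several parts of that reply stand.

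- **Few records may qualify.** If even the start year is known, the date is partial and the other sentence applies. Protocol inclusion criterion 8 calls for informant interview and review of available medical records for stimulant-treated children, so a start year will often be obtainable.
- **The listing may correct the impression.** Stop dates are collected, and SAP 3 says all study data will be listed by subject, so a reader could see a pre-dose stop. The frequency table offers no such check.
- **Other sources address prohibited use more directly.** These are the important-deviation summary, the listing of all deviations, and urine drug screens on Day 1, Day 15 and at end of study. The screening panel in Protocol Appendix III includes amphetamines but does not name methylphenidate.

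A reader might infer two stronger things, and the documents support neither. The first is that the label distorts the per-protocol population or sends false flags to the team adjudicating deviations. Important deviation 3 in SAP 4.5 asks whether the child actually took a prohibited drug between screening and end of study, subject to clinical adjudication. Nothing routes the SAP 5.1 label into that decision. The second is that the primary comparison is contaminated. The ANCOVA in SAP 7.5.1 uses treatment, baseline score and site, and no medication label enters it.

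None of this makes the classification correct. It limits the consequence to the table and to the placing of records in the concomitant listing.

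**Conclusion.** The point holds in a narrow form. For any record with a wholly missing start date and a known stop before the first dose, SAP 5.1 returns a label that its own definitions exclude. The result is a false count in the concomitant-medication table by treatment group and a misplaced entry in the concomitant listing.

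The size is unknown. The expected number of affected stimulant users is children randomized × share entering on a stimulant × share of those with no start date at all and a recorded pre-dose stop. Only the first factor is in the documents (about 100 planned), so any count would rest on assumed rates.

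The conclusion assumes that the sentence is programmed as written and that the stop date is recorded. It changes no efficacy estimate, test or analysis population. This is a minor correction to descriptive safety reporting, worth making because the error is certain where it occurs and easy to remove.

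**What to change.** Replace the last date-handling sentence of SAP 5.1 with wording such as:

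> A medication with no start day, month or year is classed as prior and as concomitant, unless its stop date is known to be before the first date of study drug, in which case it is classed as prior only.

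The exception should say before, not on or before. A drug both started and stopped on the first dosing date is concomitant under the third definition, so with its start date missing the conservative assumption should still apply to a Day 1 stop.

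The cost is one sentence and one programming condition. No new data are needed, and the change can be made before the SAP is signed and the database unblinded.

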## **5.2 Medical History**

Medical history will be coded using MedDRA Version 19.0. The count and percentage of subjects under each history term, coded by system organ class (SOC) and preferred term (PT) will be summarized descriptively by treatment group using the safety population. The SOC terms and PTs will be presented in decreasing order of the total number of subjects (frequency) who experienced each history term. System organ class terms and PTs with the same frequency will be presented alphabetically. Medical history information will also be provided in a listing by subject.

## **5.3 Psychiatric History**

Psychiatric history will be summarized by DSM-5 code and disorder. The count and percentage of subjects under each DSM-5 code and disorder will be summarized by treatment group using the safety population. The summary will be presented in decreasing order of the total number of subjects (frequency) who experienced each psychiatric diagnosis. Psychiatric history information will also be provided in a listing by subject.

ADHD diagnostic history information, including ADHD subtype and date of diagnosis, will be provided in a listing by subject.

## **5.4 Family Psychiatric History**

Family psychiatric history, as reported by the parent/guardian, will be summarized by DSM-5 disorder. The count and percentage of subjects in the safety population with any first degree relative (biological parent or sibling) considered to have a DSM-5 disorder will be summarized under the DSM-5 disorder deemed most appropriate by the rater. The summary will be presented in decreasing order of the total number of subjects (frequency) with any first degree relative who experienced each psychiatric diagnosis. Family psychiatric history information will also be provided in a listing by subject, including which first degree relative had the diagnosis.

## **6. MEASUREMENT OF TREATMENT COMPLIANCE**

Compliance with study drug will be monitored closely and determined at each visit. Subjects and their parent(s)/legal guardian(s) will be instructed to bring all unused study drug with them to the Day 15 visit. Compliance will be assessed by counting capsules and dividing the actual number of doses taken (per capsule count) by the number of doses the subject should have taken within a visit period and multiplying by 100. Subjects who miss more than 25% of scheduled doses or take more than 125% of the scheduled doses will be considered noncompliant. Treatment compliance (number of missed days) and treatment exposure (e.g. time in trial, time on treatment) will be tabulated overall and by the following groups: <75%, 75%-125%, and >125%. Subjects who are lost to follow-up and/or subjects who do not return unused study drug will have missing compliance data.

Each subject's compliance and treatment exposure data will be listed.

## **7. EFFICACY EVALUATION**

### **7.1 Overview of Efficacy Analysis Issues**

#### **7.1.1 Handling of Dropouts or Missing Data**

The SKAMP scale is a 13-item independent observer rating of subject impairment of classroom observed behaviors. Each item is rated on a 7-point impairment scale (0 = normal to 6 = maximal impairment). The combined scores for the SKAMP (SKAMP-CS) are obtained by summing the values of corresponding items in the assessment. The mean SKAMP-CS over the entire visit is derived from the SKAMP-CS at the individual 7 time points.

Missing data could occur under either or both of the following scenarios: (1) missing or invalid data for individual items in the SKAMP for a specific assessment; and (2) missing SKAMP-CS at individual time points. The approach to handling missing data under these scenarios is described below.

##### **7.1.1.1 Missing Individual Items in the SKAMP Scale**

Missing or invalid data for individual items will be handled by rules specific to the validated SKAMP scale as follows:

- If 3 or more individual items in the SKAMP have missing or invalid data, the SKAMP-CS will be set to missing.
- If 1 or 2 individual items in the SKAMP are missing or invalid, the values for the missing individual items will be imputed using the mean of the non-missing individual items for the particular subject at that visit and time point, rounded to the nearest integer.
- If any item within a SKAMP subscale is missing or invalid, the entire subscale score will be set to missing.

##### **7.1.1.2 Missing SKAMP Combined Scores at Individual Time Points**

###### **Primary Analysis**

Subjects with missing SKAMP-CS data at all individual time points at either the baseline or Day 15 visit will not be included in the primary analysis. If 3 or more time points have missing or invalid SKAMP-CS data, the mean SKAMP-CS will be set to missing. If one or two time points have missing or invalid SKAMP-CS data, the mean SKAMP-CS will be calculated as the average of the SKAMP-CS at the remaining 5 or 6 time points. No imputation of missing SKAMP-CS at individual time points will be done for the primary efficacy analysis.

## **Sensitivity Analyses**

To explore the robustness of the primary efficacy analysis of the change from baseline at Day 15 in ADHD symptoms in mean SKAMP-CS, two sensitivity analyses of the primary analysis may be performed: a placebo-based multiple imputation (MI) pattern-mixture model (PMM) analysis and a tipping point analysis using the PMM.

### **Sensitivity analysis one: Placebo-based MI PMM**

To explore the robustness of the primary analysis results, a sensitivity analysis will be carried out that assesses the situation where the data are not missing at random (NMAR). More specifically, all subjects taking dasotraline who discontinue for any reason will be assumed to behave like placebo subjects.

A controlled, multiple imputation approach based on PMM will be applied for those subjects on dasotraline using the 'Copy Reference' approach [3]. More specifically, missing data for those subjects taking dasotraline who discontinued will be imputed based on the posterior distribution of the placebo group. Missing data for placebo subjects who discontinued will also be imputed using the observed values of the placebo group.

Data will be imputed using SAS PROC MI (v9.3 or later) using the full conditional specification method (FCS). 200 burn-in iterations will be performed prior to each imputation. The imputation model will include clinical site, observed non-missing baseline mean SKAMP-CS, observed non-missing baseline PERMP scores, age, and sex. One hundred imputed datasets will be generated for analysis.

The same model used in the primary analyses will be fit to each of the 100 datasets. The parameter estimates and standard errors will be combined using PROC MIANALYZE in SAS v 9.3 or higher.

### **Sensitivity analysis two: Tipping Point Analysis using PMM**

The goal of the tipping point analysis is to determine how robust the results of the primary analysis are to varying its assumption that the change from baseline at Day 15 mean SKAMP-CS for subjects that discontinue from the dasotraline group is the same as the completers in the dasotraline group. In particular, this analysis examines how altering this assumption to allow the discontinued dasotraline subjects to have worse outcomes will impact the resulting estimates of the treatment effect. This will quantify the range of values which the assumptions can take on and still provide the same conclusions as the primary analysis, giving a very direct measure of the sensitivity of the primary analysis to deviations from the assumptions using an approach that has missing values for dasotraline discontinuation subjects imputed. Missing SKAMP-CS

data in the dasotraline group will be imputed based on observed values in the dasotraline group and likewise, missing SKAMP-CS values in the placebo group will be imputed based on observed values in the placebo group.

Shift values of .05 (penalize imputed values for dasotraline subjects by 5% of the treatment difference of the primary endpoint from the primary analysis) through 1 (penalize imputed values for dasotraline subjects by 100% of the treatment difference of the primary endpoint from the primary analysis) will be applied at increments of .05 and reported. The primary analysis will be rerun for all shift values and the resulting treatment difference, 95% CI and p-value for each shift value will be reported. The higher penalty should result in a smaller treatment difference. The wider the range of values that result in no change in interpretation, the more robust the analysis results may be considered to be.

The steps to implement the tipping point analysis are as follows:

- 1) ANCOVA model will be run using all observed data and the LS mean in the Dasotraline 2mg/day group of mean change from baseline at Week 2 in SKAMP-CS will be calculated.
- 2) Missing data will be imputed based on the MAR assumption using multiple imputation procedure (PROC MI) to create 100 complete datasets with 200 burn-in iterations.
- 3) For subjects in the dasotraline dose group, the imputed values from Step 2 will be “penalized” by adding a percentage (i.e. 5%, 10%, 15%, 20%, etc. of the LS mean treatment difference) of the absolute value of the mean change calculated from Step 1; for the placebo group, no “penalty” will be taken for the imputed values.
- 4) Each newly generated complete dataset from Step 3 will be analyzed using the primary analysis ANCOVA model and results from all 100 datasets will be combined (PROC MIANALYZE) to generate inferences.
- 5) This analysis (Steps 3-4) will be repeated for a range of values (i.e. 5%, 10%, 15%, 20%, etc. of the treatment difference) until either the tipping point (where statistical significance of the treatment effect is lost) is identified or the 100% penalty is applied.

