## 2.6 Sample Size Determination

A post-hoc ANCOVA-LOCF analysis of data from the SEP360-305 laboratory classroom study was conducted to examine the effect of dasotraline 4 mg/day versus placebo in a subset of pediatric patients with ADHD aged 6-9 years old. This analysis showed an effect size in this subgroup of 0.95 (LS mean difference at Week 2 was 7.2 with a standard error of 2.2). Assuming a smaller effect size for dasotraline 2 mg/day vs. placebo than that of dasotraline 4 mg/day vs. placebo, an effect size of 0.7 was utilized for the sample size calculation.

The 0.7 effect size also derives from a data analysis showing that in a weight-adjusted dose range of 0.065 mg/kg to 0.115 mg/kg, the SKAMP effect size was observed to be 0.70. The weight adjusted dosing in the proposed study (SEP360-311) will likely range from 0.057 mg/kg to 0.125 mg/kg given that six year old females are expected to be the lightest subjects (CDC estimates 16 kg = 3rd percentile). Thus, the estimated effect size of .7 is a reasonable assumption and will be employed in the power and sample size calculation.

Therefore, assuming an effect size of 0.7 for dasotraline 2 mg/day compared to placebo on the primary efficacy endpoint of mean SKAMP-Combined score obtained from the average of 7 assessments collected across the 12 hour classroom day, 88 subjects (44 per treatment group) will provide 90% power to detect a treatment effect between dasotraline and placebo at the two-sided alpha level of 0.05, based on the two-sample t-test with equal variance procedure.

The study will target approximately 100 subjects (50 per treatment group) randomized to either placebo or dasotraline 2 mg/day in an attempt to have 88 subjects complete the trial (assuming a 12% overall dropout rate).

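### The tipping-point steps name two different penalty units, and if the unit is the treatment difference the 100% cap stops at placebo-like dropouts

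*SAP*

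**What the plan says.** SAP 7.1.1.2, sensitivity analysis two, imputes missing Day 15 outcomes within each arm and then adds a penalty to the imputed dasotraline values.

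- **Introductory text.** The grid runs from 0.05 to 1 in steps of 0.05. The top shift is described as "penalize imputed values for dasotraline subjects by 100% of the treatment difference of the primary endpoint from the primary analysis", and the bottom shift is defined in the same unit. On reporting: "The primary analysis will be rerun for all shift values". On purpose: "This will quantify the range of values which the assumptions can take on and still provide the same conclusions as the primary analysis".
- **Step 1.** After the ANCOVA on observed data, "the LS mean in the Dasotraline 2mg/day group of mean change from baseline at Week 2 in SKAMP-CS will be calculated". No step outputs the treatment difference.
- **Step 3.** The penalty is a percentage "of the LS mean treatment difference) of the absolute value of the mean change calculated from Step 1".
- **Step 5.** The percentages refer to the treatment difference again, and the loop continues "until either the tipping point (where statistical significance of the treatment effect is lost) is identified or the 100% penalty is applied".

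Sensitivity analysis one, in the same section, is the placebo-based imputation: "all subjects taking dasotraline who discontinue for any reason will be assumed to behave like placebo subjects".

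**The concern.** There are two problems, and they do not apply together.

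**Unit.** Step 3 names both the between-arm difference and the within-arm change from Step 1. A programmer who follows Steps 1 and 3 literally builds a different analysis from one who follows the introductory text and Step 5. On the same data, one program may report a tipping point and the other none.

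**Cap, if the unit is the treatment difference.** Imputation starts dasotraline dropouts at the dasotraline mean. Adding the whole treatment difference brings them to about the placebo mean, so the most severe shift roughly repeats sensitivity analysis one and the other 19 shifts are milder. What a tipping-point analysis should add is how much worse than placebo-like the dropouts must be before the conclusion changes, and this grid never asks that.

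A smaller mismatch is that the introductory text reports every shift while Step 5 stops at the tipping point. The tipping point found is the same either way.

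**Working it through.** **The plan's own figure.** SAP 2.6 has effect size 0.7, two-sided alpha 0.05 and 44 per group. The noncentral t gives 90.1% power (43 per group gives 89.4%), and 88/(1 − 0.12) = 100 randomized. The sample size reproduces and is not in question.

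**Inputs from SAP 2.6.** The earlier classroom study had an LS mean difference of 7.2 at effect size 0.95, so SD = 7.2/0.95 = 7.58 points. The planned difference is 0.7 × 7.58 = 5.31 points. The 12% overall dropout is taken as 12 missing outcomes among 100.

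**Assumed, because the documents do not give them.** The dasotraline/placebo split of the missing outcomes is 6/6, 9/3 or 12/0. The placebo change is an improvement of 2 to 6 points or a worsening of 2.

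**Algebra of the cap.** Let δ be the size of the treatment difference, m the missing fraction on dasotraline and k the multiple of δ added.

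- Expected dropout mean minus placebo mean = (k − 1)δ, which is zero at k = 1 and favourable to dasotraline at every smaller k.
- Treatment estimate = δ(1 − mk). With m = 0.12 and k = 1 this is 5.31 × 0.88 = 4.67 points.
- At planning values t = 0.7/√(2/44) = 3.28. Ignoring growth in the standard error, the tipping multiple is (1 − 1.985/3.28)/0.12, or about 3.3.

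**Algebra of the unit.** The within-arm unit is the dasotraline mean change. If placebo improves by 2 it is (5.31 + 2)/5.31 = 1.4 times δ. If placebo improves by 6 it is 11.31/5.31 = 2.1 times. If placebo worsens by 2 it is 3.31/5.31 = 0.6 times. The two units are equal in size if placebo change is zero.

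**Simulation.** 50 per arm, arm-specific normal multiple imputation with 100 imputations and no covariates, Rubin's rules with small-sample degrees of freedom, 4,000 trials per scenario. The 0.7 and 0.5 rows below pool two such runs. Denominators are trials with a significant primary result.

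| Treatment-difference unit | 6/6 | 9/3 | 12/0 |
|---|---|---|---|
| Tips by 100%, effect 0.7 | 491/7,238 = 6.8% | 880/7,253 = 12.1% | 1,441/7,170 = 20.1% |
| Tips by 100%, effect 0.5 | 921/5,100 = 18.1% | 1,475/5,068 = 29.1% | 2,043/4,982 = 41.0% |
| Tips by 100%, effect 0.4 | 446/1,827 = 24.4% | 714/1,838 = 38.8% | 946/1,774 = 53.3% |
| Median tipping multiple, effect 0.7 | 2.95 | 2.1 | 1.6 |
| Same verdict at 100% as placebo-based imputation, effect 0.7 | 98.9% | 97.5% | 95.8% |

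Estimates from the 100% shift and from placebo-based imputation differed on average by 0.04 to 0.07 points. The results that the grid can resolve have a primary p above roughly 0.026, 0.017 and 0.011 for the three splits. These bounds are approximate: 12%, 11% and 16% of the trials that tipped had a smaller p.

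Unit comparison at effect 0.7, one run, with denominators 3,617, 3,601 and 3,578:

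| Tips at 100% | 6/6 | 9/3 | 12/0 |
|---|---|---|---|
| Treatment-difference unit | 250 = 6.9% | 414 = 11.5% | 686 = 19.2% |
| Within-arm unit, placebo improves 2 | 521 = 14.4% | 900 = 25.0% | 1,364 = 38.1% |
| Within-arm unit, placebo improves 6 | 1,014 = 28.0% | 1,802 = 50.0% | 2,539 = 71.0% |
| Within-arm unit, placebo worsens 2 | 159 = 4.4% | 248 = 6.9% | 350 = 9.8% |
| Units disagree, placebo improves 2 | 271 = 7.5% | 486 = 13.5% | 678 = 18.9% |
| Units disagree, placebo improves 6 | 764 = 21.1% | 1,388 = 38.5% | 1,853 = 51.8% |

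A separate simulation of 1,500 trials per scenario gave 6.6%, 13.0% and 19.9% for the first row, in agreement.

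**The case against.** The strongest reply on the unit is that the intent is plain. The introductory text (twice), the parenthesis in Step 3 and Step 5 all say treatment difference, SAP 7.5.1 already produces that quantity, and the pointer to Step 1 is a drafting slip. That is the likelier reading, and once it is written down the unit disagreement disappears. As drafted, though, Steps 1 and 3 are the executable instructions and point to another quantity.

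On the cap, Step 5 expressly allows the procedure to end at 100%, and the SAP treats robustness as a matter of degree. The grid is valid over its stated range and informative for borderline results. What survives is that its stated purpose promises more than it delivers, because the end of the grid nearly repeats sensitivity analysis one.

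On size, the placebo change and the splits are assumed, and 12/0 is extreme. A completer must attend both Visits 5 and 6 (SAP 2.2), so some dropouts will have a Day 15 outcome. With only 3 missing per arm, the unit disagreement falls to about 3% to 8%. Fewer missing values also mean fewer trials tip within the cap (about 2% at 3/3), so this weakens the unit point and not the cap point. The simulated imputation omits the covariates that the SAP lists for sensitivity analysis one, so the agreement percentages are approximate.

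Finally, SAP 7.1.1.2 makes both sensitivity analyses optional. Protocol 15.3.8 commits to them.

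**Conclusion.** The concern holds and should be corrected, although it does not threaten the primary result. The contradiction over the unit is on the page and depends on no assumption. The cap result follows from the algebra, in expectation, once the treatment difference is the unit.

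At the planned effect, with 12 missing outcomes, about 80% to 93% of significant trials would end with no tipping point found. The range that the SAP says it will quantify would then be known only to reach about placebo-like. The share depends on the assumed split and on the true effect: at effect 0.4 with 12/0, about half of significant trials do tip within the grid. The size of the unit disagreement rests on an assumed placebo change and vanishes if that change is zero.

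**What to change.** 1. Have Step 1 output the LS mean treatment difference, and use its absolute value as the only penalty unit in the introductory text and Steps 3 to 5.
2. Keep the shifts from 0.05 to 1.00, then continue in steps of 0.25 until significance is lost or a prespecified limit is reached.
3. State and justify that limit in SKAMP points. One example is the observed difference plus one SD, meaning dropouts who average one SD worse than placebo. At planning values this is 5.3 + 7.6 = 12.9 points, or 12.9/5.3 = 2.4 times the difference. With that limit, 34%, 63% and 87% of significant trials at effect 0.7 would tip for the 6/6, 9/3 and 12/0 splits (1,233/3,617, 2,257/3,601 and 3,099/3,578).
4. Report the tipping multiple and the corresponding shift in points, or that none was found up to the limit. Report it as not applicable if no dasotraline value is imputed.
5. Report every shift, as the introductory text says, and align Step 5 with it.

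The cost is a few lines of SAP text and, with the example limit, about 4 to 8 more output rows from a program that is needed anyway. The primary analysis and the sample size do not change.
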